9.7.2. Descriptive Statistics

For demographic and baseline variables and duration of Mysimba/Contrave use (measured as both continuous treatment of the initial Mysimba/Contrave duration and the total treatment duration of Mysimba/Contrave), descriptive statistics will be used to describe continuous variables, (e.g., mean, standard deviation, median, quartiles 1 and 3, minimum, maximum, and two-sided 95% confidence intervals [CI]). Categorical variables will be described by the total and percentage of each response and the number of missing data (data that are unavailable in the database).

Patterns of Mysimba/Contrave use will be described by mean (standard deviation, SD) and median (quartile1, quartile 3) number of prescriptions per patient, number and duration of treatment episodes per patient as well as the average duration between prescription episodes. Analyses will be performed for all users of Mysimba/Contrave, including an assessment of whether the subjects have adhered to the prescribed treatment with Mysimba/Contrave according to the terms of the SmPC (adapted to the local country SmPC for the data source as needed, and adapted if BMI is not accessible). The number and proportion of patients who received treatment with Mysimba/Contrave will be provided according to the following subgroups (availability of variables to be summarized in SAP):

(a) Inconsistent with labelled indication:

- 1) Age < 18 years
- 2) Use other than management of weight
- 3) Management of weight in a patient who does not have obesity or is not overweight and has a weight-related comorbidity
- 4) A prescribed maintenance dose other than the Mysimba/Contrave 32mg/360mg
- 5) Continued use past 16 weeks without \geq 5% weight loss
 - (b) Incompatible with the stated contraindications set out in the SmPC:
- 1) A current diagnosis of uncontrolled hypertension, seizure disorder (or history of seizures), or end-stage renal failure
- 2) A history bipolar disorder, anorexia nervosa or bulimia
- 3) A current dependence on chronic opioids or opiate agonists (e.g., methadone)
- 4) A current state of acute opiate withdrawal
- 5) Any concomitant treatment containing bupropion, naltrexone, or a MAOI
- 6) Patients with a known central nervous system tumour
- 7) Patients undergoing acute alcohol or benzodiazepine withdrawal
- 8) Patients with severe hepatic impairment

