Name of the main author of the protocol.				
Name of the main author of the protocol:				
Date: dd/Month/year				
Signature:				

15. Appendix 2. Code lists

Mysimba ATC: A08AA62 Contrave NDC: search terms – Contrave, naltrexone, bupropion Naltrexone ATC: N07BB04, A06AH01, N02AA56	
Contrave NDC: search terms – Contrave, naltrexone, bupropion	
Naltrexone ATC: N07BB04, A06AH01, N02AA56	
NDC: search terms – naltrexone	
Bupropion ATC: N06AX12	
NDC: search terms – bupropion	
Concomitant Medications	
CYP2B6 inhibitors See Appendix 2A	
CYP2B6 inducers See Appendix 2A	
CYP2B6 substrates See Appendix 2A	
CYP2D6 substrates See Appendix 2A	
Drugs that lower Propoxyphene, remifentanil, sufentanil, tapentadol, tramadol,	
seizure threshold baclofen, buspirone, dalfampridine, lithium, mefenamic acid,	
amphetamine, benzphetamine hydrocholoride, dextroamphetan	mine,
hydroxyamphetamine hydrobromide, lisdexamfetamine dimes	
methamphetamine hydrochloride, cocaine, phenylpropanolam	
dexamphetamine, methylphenidate	
Opioid or opiate ATC: N02A;	
agonist	
Opium alkaloids & ATC: R05DA, N02AA	
derivatives	
MAOI ATC: N04BD, N06AF, N06AG	
Seizures ICD-10: G40	
Increase in blood ICD-10: R00.0, R03.0	
pressure or heart rate	
Hypersensitivity, ICD-10: T78, L51	
including Stevens-	
Johnson	
Serotonin syndrome ICD-10: T43.225A	
Suicidality ICD-10: R45.851, T14.91	
Diabetes ICD-10: E10-E11	
Dyslipidaemia ICD-10: E78	
Neuropsychiatric	
conditions:	
Mania ICD-10: F30	
Bipolar disorder ICD-10: F31	

N4 : 1 :	ICD 10 F22
Major depressive	ICD-10: F33
disorder	ICD 10 F50 0
Anorexia nervosa	ICD-10: F50.0
Bulimia	ICD-10: F50.2
Hypertension	ICD-10: I10-I16
TT . 11 1	
Uncontrolled	ICD-10: I10-I16 (with Systolic ≥140 mmHg or diastolic ≥90 mmHg)
hypertension	10D 10 N10 0 N10 5
Moderate or severe	ICD-10: N18.3-N18.5
renal impairment	
End stage renal	ICD-10: N18.6
disease	
Hepatic impairment	ICD-10: K70, K72-K75
Central nervous	ICD-10: C72
system tumour	
Substance	ICD-10: F10-F19
abuse/dependency	
	ATC: N06AA11
Protriptyline*	NDC: search terms – protriptyline
Dannanidal (Anarril)*	ATC: N05AD07
Benperidol (Anquil)*	No NDC
Flupentixol	ATC N05AF01
(Depixol)*	No NDC
Fluphenazine	ATC: N05AF02
(Modecate,	NDC: search terms – fluphenazine
Prolixin)*	•
Levomepromazine	ATC: N05AA02
(Nozinan)*	No NDC
Loxapine	ATC: N05AH01
(Loxitane)*	NDC: search terms – loxapine
	ATC: N05AE02
Molindone (Moban)*	NDC: search terms – molindone
	ATC: N05AC01
Periciazine*	No NDC
Sulpiride (Dolmatil,	ATC: N05AL01
Sulpor)*	No NDC

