Upadacitinib	NDC: search terms- upadacitinib
X 7 11 '	ATC: N07XX13
Valbenazine	NDC: search terms- valbenazine
** 10 .	ATC: N06AX23, N06AX16
Venlafaxine	NDC: search terms- venlafaxine
	ATC: C01BG11
Vernakalant	No NDC
	ATC: N06AX24
Vilazodone	NDC: search terms – vilazodone
	ATC: N06AX26
Vortioxetine	NDC: search terms – vortioxetine
	ATC: G04BE04
Yohimbine	No NDC
	ATC: N05CF02
Zolpidem	NDC: search terms – zolpidem
Zuclopenthixol	ATC: N05AF05
(Clopixol, Clopixol	No NDC
Acuphase, Clopixol	
Concentrate)	
Buprenorphine	ATC: N02AE01, N07BC01, N07BC51
Duprenorphine	NDC: search terms – buprenorphine
Hydrocodone	ATC: R05DA03
Trydrocodone	NDC: search terms – hydrocodone
Methadone	ATC: N07BC05, N07BC02, N02AC52, R05DA06
Methadone	NDC: search terms – methadone
	ATC: N07BC06, R05DA01, S01XA06, N02AA01, N02AG01,
Morphine*	A07DA52, N02AA51, N02AA04, R05DA05
	NDC: search terms – morphine sulphate
	ATC: N02AA, R05DA, R05FA, A07DA02, N02AA02, R05DA05,
Opium	R05FA02, R05FA01
1	NDC: search terms – belladonna and opium
	ATC: N02AA05, N02AJ17, N02AJ18, N02AJ19, N02AA55,
Oxycodone	N02AA56
	NDC: search terms – oxycodone
0 1	ATC: N02AA11
Oxymorphone	NDC: search terms – oxymorphone
T 1.1	ATC: N02AX02, N02AJ13, N02AJ14, N02AJ15, N02AJ16
Tramadol	NDC: search terms – tramadol
	1 - := - :

16. Appendix 2a

CYP2B6	CYP2B6 inducers	CYP2B6 substrates	CYP2D6
inhibitors			
Abametapir	Cenobamate	Cenobamate	4-Methoxyamphetamine
Abemaciclib	Clotrimazole	Enasidenib	5-methoxy-N,N-
Amlodipine	Dabrafenib	Fexinidazole	dimethyltryptamine
Amprenavir	Enasidenib	Medical Cannabis	Acebutolol
Azelastine	Fexinidazole	Artemether	Acetaminophen
Brincidofovir	Medical Cannabis	Artemisinin	Almotriptan
Cannabidiol	Pexidartinib	Carbamazepine	Alogliptin
Cannabinol	Rifamycin	Cyclophosphamide	Alprenolol
Cenobamate	Ritonavir	Efavirenz	Aminophenazone
Cisplatin	Simvastatin	Esketamine	Amitriptyline
Clascoterone	Sorafenib	Isoflurane	Amoxapine
Clopidogrel	Alpelisib	Methadone	Amphetamine
Clotrimazole	Armodafinil	Nevirapine	Amprenavir
Colchicine	Artemether	Perampanel	Anisodamine
Crisaborole	Artemisinin	Permethrin	Antipyrine
Crizotinib	Atorvastatin	Phenytoin	Aprindine
Curcumin	Avacopan	Thalidomide	Arformoterol
Curcumin sulfate	Betamethasone	Zanubrutinib	Aripiprazole
Dabrafenib	Budesonide	Amlodipine	Aripiprazole lauroxil
Desipramine	Carbamazepine	Cannabidiol	Arotinolol
Doxorubicin	Cerivastatin	Clopidogrel	Asenapine
Dronabinol	Cyclophosphamide	Selegiline	Astemizole
Duloxetine	Dexamethasone	Sertraline	Asunaprevir

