Pentamidine	
Perhexiline	
Perospirone	
Perphenazine	
Phenacetin	
Phenformin	
Phenytoin	
Pimavanserin	
Pimozide	
Pindolol	
Piperazine	
Pipotiazine	
Pirfenidone	
Pitolisant	
Ponatinib	
Practolol	
Pralsetinib	
Procainamide	
Prochlorperazine	
Progesterone	
Promazine	
Promethazine	
Propacetamol	
Propafenone	

Propranolol
Quetiapine
Quinine
Ranolazine
Remdesivir
Remoxipride
Repinotan
Revefenacin
Ripretinib
Risperidone
Ritonavir
Rotigotine
Rucaparib
Rupatadine
Selegiline
Sertindole
Sertificitie
Sertraine
Simvastatin
Solifenacin
Sotalol
Sparteine
Tafenoquine
Talinolol
Tamoxifen
Tamsulosin
Tapentadol
Tapinarof
Tegaserod
Terfenadine
Tertatolol
Tesmilifene
Tetrabenazine
Theophylline
Thioridazine
Ticlopidine
Timolol
Tiotropium
Tipranavir
Tolterodine
Trabectedin
Tramadol
Trazodone
Triclabendazole
Trimipramine
Umeclidinium
Umifenovir
Upadacitinib
Valbenazine
Venlafaxine
Vernakalant
Vilazodone
Viloxazine
Vortioxetine
Yohimbine
Zolpidem
Zuclopenthixol
Zaciopericiixoi

Opioids

Acetaminophen/Caffeine/Dihvdrocodeine bitartrate

Acetaminophen/Codeine Phosphate

Acetaminophen/Oxycodone Hydrochloride

alfentanil

Alfentanil Hydrochloride

Aspirin/Caffeine/Dihydrocodeine Bitartrate

Aspirin/Codeine Phosphate

Aspirin/Oxycodone Hydrochloride

Belladonna/Opium

Benzhydrocodone/Acetaminophen

bezitramide

Buprenorphine

Buprenorphine Hydrochloride

Buprenorphine/Naloxone

Butalbital/Acetaminophen/Caffeine/Codeine Phosphate

Butalbital/Aspirin/Caffeine/Codeine Phosphate

Butorphanol Tartrate

butorphanol

Carisoprodol/Aspirin/Codeine Phosphate

Celecoxib/Tramadol Hydrochloride

Chlorpheniramine Polistirex/Codeine Polistirex

codeine

codeine and acetylsalicylic acid

codeine and ibuprofen

codeine and other non-opioid analgesics

codeine and paracetamol

Codeine Phosphate/Guaifenesin

Codeine Sulfate

codeine, combinations excl. psycholeptics

codeine, combinations with psycholeptics

dextromoramide

dextropropoxyphene

dextropropoxyphene, combinations excl. psycholeptics

dextropropoxyphene, combinations with psycholeptics

dezocine

Difelikefalin

Difenoxin Hydrochloride/Atropine Sulfate

dihydrocodeine and acetylsalicylic acid

dihydrocodeine and other non-opioid analgesics

dihydrocodeine and paracetamol

dihydrocodeine

dihydrocodeine, combinations

Diphenoxylate Hydrochloride/Atropine Sulfate

Fentanyl Citrate

fentanyl

FENTANYL/DROPERIDOL

hydrocodone

Hydrocodone Bitartrate

Hydrocodone Bitartrate/Acetaminophen

Hydrocodone Bitartrate/Chlorpheniramine Maleate

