Hydrocodone bitartrate/Guaifenesin

Hydrocodone Bitartrate/Homatropine Methylbromide

Hydrocodone Bitartrate/Ibuprofen

Hydrocodone bitartrate/Pseudoephedrine Hydrochloride

Hydrocodone Polistirex/Chlorpheniramine Polistirex

Hydrocodone/Chlorpheniramine/Pseudoephedrine

Hydrocodone/Pseudoephedrine/Guaifenesin

hydromorphone hydromorphone and antispasmodics hydromorphone and naloxone Hydromorphone Hydrochloride hydromorphone ketobemidone and antispasmodics ketobemidone LEVOMETHADYL **LEVORPHANOL** Levorphanol Tartrate meperidine Meperidine Hydrochloride Meperidine Hydrochloride/Promethazine Hydrochloride meptazinol methadone Methadone Hydrochloride methadone, combinations excl. psycholeptics morphine and antispasmodics Morphine Sulfate Morphine Sulfate Liposome Morphine Sulfate/Naltrexone Hydrochloride morphine morphine, combinations Nalbuphine Hydrochloride nalbuphine nicomorphine oliceridine opium oxycodone and acetylsalicylic acid oxycodone and ibuprofen oxycodone and naloxone oxycodone and naltrexone oxycodone and paracetamol Oxycodone Hydrochloride Oxycodone Hydrochloride/Naloxone Hydrochloride Oxycodone Hydrochloride/Naltrexone Hydrochloride oxycodone Oxycodone/Ibuprofen Oxymorphone Hydrochloride oxymorphone papaveretum Paregoric pentazocine pethidine and antispasmodics pethidine pethidine, combinations excl. psycholeptics pethidine, combinations with psycholeptics phenazocine piritramide Promethazine Hydrochloride/Codeine Phosphate Promethazine/Phenylephrine/Codeine Phosphate **PROPOXYPHENE** PROPOXYPHENE NAPSYLATE/ACETAMINOPHEN remifentanil Remifentanil Hydrochloride sufentanil Sufentanil Citrate Tapentadol Hydrochloride

tapentadol
tilidine and naloxone
tilidine
tramadol and celecoxib
tramadol and dexketoprofen
tramadol and other non-opioid analgesics
tramadol and paracetamol
Tramadol Hydrochloride
Tramadol Hydrochloride/Acetaminophen
tramadol

Triprolidine/Pseudoephedrine/Codeine

Opium alkaloid and derivatives

ATC: R05A

acetyldihydrocodeine codeine combinations dextromethorphan dimemorfan ethylmorphine hydrocodone normethadone noscapine opium alkaloids with morphine pholcodine thebacon

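### The opioid class row in Appendix 2 (N02A only) leaves out most of the methadone and buprenorphine codes listed in the same appendix, and the protocol does not say which rows define the opioid contraindication

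*Protocol*

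**What the plan says.** - **The criterion.** Section 8 and section 9.7.2 (b) 3) list as a contraindication "A current dependence on chronic opioids or opiate agonists (e.g., methadone" (the closing bracket follows).
- **Where definitions come from.** Section 9.3.2 says variables are identified from pre-specified code lists and points to Appendix 2. Section 9.3.3 says the per-database definitions become final in the SAP.
- **The class row.** Appendix 2 has a row for opioid or opiate agonist, the variable also named in the notes to Figure 1, in section 9.3.2 item 4 and in Appendix 3. It reads "Opioid or opiate ATC: N02A". The adjacent row reads "Opium alkaloids & ATC: R05DA, N02AA".
- **The drug rows.** Near its end, Appendix 2 has separate rows for individual opioids. Methadone is "ATC: N07BC05, N07BC02, N02AC52, R05DA06"; buprenorphine is "ATC: N02AE01, N07BC01, N07BC51".
- **The name list.** The opioid list in Appendix 2a includes "Methadone Hydrochloride", "methadone, combinations excl. psycholeptics" and "Buprenorphine Hydrochloride".
- **The diagnosis route.** Section 9.3.3 item 12 obtains substance abuse and dependency from ICD-10 codes, given in Appendix 2 as F10-F19. Appendix 3 rates substance use/abuse as Limited in all five countries.

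**The concern.** The row that carries the variable's own label leaves out most codes for the drug that the criterion gives as its example. Appendix 2a names that drug as a member of the class. The same variable therefore has two memberships within one protocol.

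The criterion feeds primary objective 2, the number and percentage of users compliant with the SmPC. It also feeds the compliant versus non-compliant split on which AESI incidence is compared (section 8 and section 9.7.3.1). Nordic medication use is identified by ATC code (sections 9.3.2 and 9.3.3), and patient-level data are analysed inside each country by separate teams (sections 9.6 and 9.8). A team that programs the labelled row and a team that uses the drug rows or the name list could classify the same patient differently, with no sign of it in the output.

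**Working it through.** No sample size or precision figure is involved. The check is a prefix match of the drug-row codes in Appendix 2 against the class rows in the same appendix.

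**Inputs (all from Appendix 2)**
- Class row: N02A. Adjacent row: R05DA, N02AA.
- Methadone, 4 codes: N07BC05, N07BC02, N02AC52, R05DA06.
- Buprenorphine, 3 codes: N02AE01, N07BC01, N07BC51.
- Morphine row, for the remaining N07BC code: N07BC06.

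**Result**

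| Definition used | Methadone | Buprenorphine | N07BC codes outside |
|---|---|---|---|
| N02A only | 1 of 4 (N02AC52) | 1 of 3 (N02AE01) | 01, 02, 05, 06, 51 |
| N02A + R05DA | 2 of 4 (adds R05DA06) | 1 of 3 | 01, 02, 05, 06, 51 |
| N02A + the five N07BC codes | 3 of 4 | 3 of 3 | none |
| N02A + R05DA + the five N07BC codes | 4 of 4 | 3 of 3 | none |

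The adjacent row's other code, N02AA, already lies within N02A and adds nothing. Using the drug rows alongside the class row also gives 4 + 3 = 7 of 7 codes.

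**Does the text tell the analyst to use the drug rows?**
1. The four CYP rows of Appendix 2 send the reader to Appendix 2A. The opioid class row does not.
2. The closing block of drug rows covers buprenorphine, hydrocodone, methadone, morphine, opium, oxycodone, oxymorphone and tramadol. Seven of these eight, all but morphine, also stand in the CYP2B6 or CYP2D6 columns of Appendix 2a. The block may therefore serve the CYP variables, and nothing ties it to the opioid variable.
3. Section 9.3.3 item 14 cites Appendix 2 and 2A together, but for prior medication at baseline. The concomitant-medication item in section 9.3.2 has no such pointer.
4. The neighbouring variable shows the same kind of mismatch. Opium alkaloids are coded R05DA and N02AA in Appendix 2, but their list in Appendix 2a is headed R05A.

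The protocol therefore states one code for the labelled variable, lists more codes and names elsewhere, and gives no rule for combining them.

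**The case against.** The strongest reply is that the codes are not absent. Appendix 2 as a whole is the definition source, and its methadone and buprenorphine rows are ATC definitions that include the N07BC codes. Morphine sits in the closing block without being on any CYP list, which suggests that the block is more than a CYP expansion. Section 9.3.3 points to both appendices for prior medication, and read together they cover all seven codes. The criterion concerns dependence, which also has a diagnosis route through F10-F19, and no passage says that the N02A row alone decides (b) 3). The row ends in a semicolon in a table that may have lost text when it was read from PDF. Final definitions are left to the SAP.

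Much of this stands, and it rules out several stronger readings that a reader might infer:
- **That these patients are missed.** They would be missed by the medication variable only if it were programmed from the labelled row. The protocol neither requires nor excludes that.
- **That Nordic sensitivity is 0%.** A count of codes is not a share of patients, and the protocol gives no dispensing counts by code.
- **That US data would flag these patients while Nordic data would not.** The class row shows no NDC term, and Appendix 2a is not labelled as US-only.
- **That these are the most clearly contraindicated patients.** The protocol does not rank contraindicated users, and it does not describe what the N07BC group is for.

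The reply does not remove the inconsistency. The protocol states a code for this variable, and that code disagrees with the drug rows and the name list in its own appendices. The diagnosis backstop is weak: Appendix 3 expects under-recording of substance use, and section 9.4.1 names substance use and dependence among the items prone to misclassification. Deferring final definitions to the SAP explains an absent detail, but not a stated code that leaves out most codes for the criterion's own example drug.

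**Conclusion.** The point holds as an internal inconsistency that should be corrected. N02A contains 1 of 4 methadone codes (2 of 4 with the adjacent R05DA row), 1 of 3 buprenorphine codes and none of the five N07BC codes in the appendix, while the criterion names methadone and Appendix 2a lists both drugs as opioids.

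The consequence is conditional. If the Nordic variable is built from its labelled row, patients dispensed these drugs only under N07BC codes would not be flagged by the opioid medication variable. They could be counted as compliant unless an F10-F19 diagnosis, or another ground for non-compliance, is recorded. How many patients this concerns cannot be derived from the protocol.

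The conclusion assumes that the class row as printed is complete and that no rule elsewhere combines the rows; the protocol contains none. It does not extend to saying that an overlapping N07BC dispensing is by itself enough to meet (b) 3), since the criterion is worded as dependence.

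**What to change.** 1. Add N07BC01, N07BC02, N07BC05, N07BC06 and N07BC51 to N02A in the class row of Appendix 2, all taken from the appendix's own drug rows.
2. Reconcile the class row with the Appendix 2a opioid list, so that the ATC codes and the drug names describe the same set. Reconcile the opium alkaloid codes at the same time.
3. State which rows together define criterion (b) 3): the class row, the opium alkaloid row (which holds methadone's remaining code, R05DA06), the drug rows and the F10-F19 diagnoses. State also how dispensing and diagnosis combine to indicate dependence.

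This is an edit to a code list and one sentence of definition. Section 9.6 already plans to obtain the healthcare-transactional data of all users, so no new data source should be needed. Any interim output already produced from the class row would have to be rerun for this criterion and for the compliance split.

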8. RESEARCH QUESTIONS AND OBJECTIVES

The aim of the study is to assess the long-term (548 days) real-world utilization patterns of Mysimba/Contrave use among patients who are prescribed Mysimba/Contrave. There are no a priori hypotheses for this study.

The primary objectives of the study are:

- To describe demographic and baseline characteristics of patients initiating use of Mysimba/Contrave; and
- 2. To evaluate patterns of Mysimba/Contrave initiation and use, including number of prescriptions, number of treatment episodes and duration between prescriptions, as well as estimating the number and percentage of patients compliant and non-compliant with the SmPC.

Analysis of compliance to the labelled indication and contraindications will be adapted to the specific SmPC for the country relevant to the data source (s). Examples of non-compliance include, but are not limited to:

Use inconsistent with labelled indication:

- 1. Age <18 years
- 2. Use other than management of weight
- 3. Management of weight in a patient who does not have obesity or is not overweight and has a weight-related comorbidity
- 4. A prescribed maintenance dose other than the Mysimba/Contrave 32mg/360mg
- 5. Continued use past 16 weeks without \geq 5% weight loss

Use in patients with contraindications:

- 6. A current diagnosis of uncontrolled hypertension, seizure disorder (or history of seizures), or end-stage renal failure
- 7. A history of bipolar disorder, anorexia nervosa or bulimia
- 8. A current dependence on chronic opioids or opiate agonists (e.g., methadone)
- 9. A current state of acute opiate withdrawal
- 10. Any concomitant treatment containing bupropion, naltrexone, or a MAOI
- 11. Patients with a known central nervous system tumour

Proprietary and Confidential:

- 12. Patients undergoing acute alcohol or benzodiazepine withdrawal
- 13. Patients with severe hepatic impairment (dependent on local SmPC)

The secondary objectives of this study are:

- 1. To assess and compare the observed incidence of AESIs in usual clinical practice among users of Mysimba/Contrave compliant and non-compliant with the SmPC. AESIs include new onset of the following:
 - 1. Seizures
 - 2. Suicidality (i.e., suicidal ideation, attempted suicide or completed suicide)
 - 3. Neuropsychiatric events (i.e., mania or depression)
 - 4. Hepatotoxicity
 - 5. Severe hypersensitivity reaction
 - 6. Serotonin syndrome

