9.3.2. Outcomes

When available, the following variables will be collected after initiation of Mysimba/Contrave (Post-Index Date). A draft listing of variables available in each country is included in Appendix 3 and will be included as final in the Statistical Analysis Plan (SAP).

Proprietary and Confidential:

This document cannot be used, distributed, or reproduced in any way without the prior written consent of Currax Pharmaceuticals LLC.

- 1. BMI, height, and weight prior to index date, the date of initiation of the medication(s) of interest, (obtained directly from data sources; BMI may be calculated if height and weight available). In the event that BMI and/or weight are not available through licensed access to the Scandinavian National Patient Registries, an attempt will be made to identify the obese population through diagnosis codes or procedures such as counseling for weight loss. It should be noted that this approach may identify a more obese and more motivated population than what would be identified on the basis of BMI. In addition, an approach may be implemented to predict BMI or apply published algorithms predicting BMI. Details will be laid out in the SAP.
- 2. Weight will be obtained if available 16-24 weeks post-index date to evaluate use inconsistent with labelled indication. BMI after index date will be obtained in the same timeframe, if available.
- 3. Relevant comorbidities (obtained via ICD-10 codes):
 - 1. Weight-related comorbidities (i.e., type 2 diabetes, dyslipidaemia, hypertension)
 - 2. Neuropsychiatric conditions (mania, bipolar disorder, major depressive disorder [MDD], anorexia nervosa, bulimia)
 - 3. Uncontrolled hypertension
 - 4. Moderate or severe renal impairment
 - 5. End-stage renal disease
 - 6. Seizure disorder
 - 7. Hepatic impairment (defined by Child-Pugh score category)
 - 8. Central nervous system tumour
- 4. Concomitant medication use, including: naltrexone, bupropion, CYP2B6 inhibitors, CYP2B6 inducers, CYP2B6 substrates, CYP2D6 substrates, drugs that lower seizure threshold, opioid or opiate agonist, or MAOI (obtained via ATC [outpatient, Nordic data] or NDC [US data])
- 5. Pregnancy status and breastfeeding status (obtained via ICD-10 codes)
- 6. AESIs (obtained via ICD-10 codes):
 - 1. Seizures

- 2. Suicidality (i.e., suicidal ideation, attempted suicide or completed suicide)
- 3. Neuropsychiatric events (i.e., mania or depression)
- 4. Hepatotoxicity
- 5. Severe hypersensitivity reaction

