- 6. Serotonin syndrome
- 7. Major adverse cardiovascular events (i.e., cardiovascular-related death, non-fatal myocardial infarction, or non-fatal stroke)

Deaths will also be described by treatment group, for those with vital status available.

- 7. Treatment discontinuation (assessed using ATC [outpatient, Nordic data] or NDC [US data])
- 8. Reason(s) for treatment discontinuation (obtained via ICD-10 codes in the 90 days prior to discontinuation)

All variables will be identified from the data sources via a pre-specified list of definitions (i.e., code lists; see Appendix 2). Occurrence of AESI based on diagnostic codes will be summarized for all patients, and for a subgroup of patients who do not adhere to conditions of the EU SmPC for the Scandinavian countries (adapted to local SmPC as needed) or to the FDA SmPC for the US. Such criteria include: not meeting appropriate criteria for the indication [obese (BMI \geq 30 kg/m²), or being overweight (BMI \geq 27 kg/m² to < 30 kg/m²) and having at least one weight-related co-morbidity (e.g., type 2 diabetes, controlled hypertension, or dyslipidemia) based on diagnostic codes. If BMI is not available, diagnostic and procedure codes for obesity and weight loss will be applied, recognizing that it will likely produce a more obese population than would be identified by BMI. Subgroup analyses will also be conducted to assess continuous treatment in patients with either renal or hepatic impairment.

Initiation of specific medications that could result with the occurrence of an event corresponding to an AESI (e.g., newly initiating anti-epileptic/seizure medication, newly initiating medications indicated for mania or depression) will also be tabulated. For hepatotoxicity, liver function tests can be used (when available) in addition to diagnostic codes.

For reason(s) patients who discontinue treatment (i.e., do not refill their prescription), events (potential AESIs and contraindications) and clinical status (magnitude of weight loss or gain)

Proprietary and Confidential:

occurring within the 90-day window prior to discontinuation will be summarized. It should be noted that weight may not be available in the Scandinavian registries.

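### The Appendix 2 code list does not match the new-onset AESIs: seizures, depression, suicidality and serotonin syndrome would be under-counted, and the last two would come near zero in the Nordic registers because of coding

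*Protocol*

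**What the plan says.** Section 8, under the first secondary objective, states that "AESIs include new onset of the following" and lists, among others, seizures, suicidality, mania or depression, and serotonin syndrome. Section 9.3.2 gives the route of ascertainment, "AESIs (obtained via ICD-10 codes", and ties it to the appendix: "All variables will be identified from the data sources via a pre-specified list of definitions (i.e., code lists; see Appendix 2". It also spells out one composite: "Suicidality (i.e., suicidal ideation, attempted suicide or completed suicide".

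The Appendix 2 rows are:

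- "Seizures ICD-10: G40". This is the only seizure row.
- "Mania ICD-10: F30", followed by bipolar disorder and then major depressive disorder with F33. No row is labelled depression.
- "Suicidality ICD-10: R45.851, T14.91".
- "Serotonin syndrome ICD-10: T43.225A".

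For many medicines Appendix 2 separates ATC entries (Nordic) from NDC entries (US). For diagnoses it gives one undivided ICD-10 entry for all five sources. Appendix 3 lists Seizure and Seizure disorder as separate variables with different availability: Yes in every source for the first; Maybe in the US and Unlikely in the Nordic sources for the second.

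**The concern.** A code list that is narrower than the event it stands for gives low counts whatever the true risk. These four AESIs feed the first secondary objective, the incidence in users compliant and non-compliant with the SmPC. The study's stated purpose includes judging whether the SmPC should be revised. Section 9.5 reads zero events in 3,000 patients as 95% confidence that the risk is at most 0.1%. That reading is sound only if the event, had it occurred, would have been coded in a way the list retrieves. If the list cannot retrieve it in a given source, a zero there says nothing about harm.

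**Working it through.** **Code against concept.** The protocol prints codes without definitions. The meanings below are those of the ICD classification that the protocol adopts.

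| AESI (section 8 / 9.3.2) | Appendix 2 | Mismatch |
|---|---|---|
| Seizures, new onset | G40 | Epilepsy category. An isolated or provoked seizure coded as a convulsion (R56) is not retrieved. One row serves two Appendix 3 variables. |
| Depression, new onset | F33, in the major depressive disorder row | Recurrent disorder. A first episode (F32) is not retrieved if this row defines the AESI. No other row could. |
| Suicidal ideation, attempt, completed suicide | R45.851, T14.91 | Ideation and attempt only; no code for completed suicide. Both codes are US clinical modification. |
| Serotonin syndrome | T43.225A | US clinical modification; an SSRI adverse-effect code, not specific to the syndrome. Appendix 3 has no row for this AESI. |

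In the US data the suicidality codes do retrieve ideation and some attempts, so the problem there is under-capture. In the Nordic registers, matching on the codes as listed would return next to nothing for suicidality and serotonin syndrome.

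**The plan's own figure.** Section 9.5: n = 3,000, no events.

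- Rule of three: 3/3,000 = 0.1000%.
- Exact one-sided 95% bound: 1 − 0.05^(1/3000) = 0.0998%.

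The stated 0.1% reproduces.

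**Effect of incomplete capture.** Let s be the fraction of true events that the codes retrieve. The documents give no value, so every s below is an assumption. The coded risk is s × p, so the bound on the true risk p is 0.0998%/s. At a true risk of 0.1%, the chance of seeing no coded event is (1 − 0.001 × s)^3000.

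| s (assumed) | Bound on true risk | P(no coded event), true risk 0.1% | Expected coded events, 3 × s |
|---|---|---|---|
| 1 | 0.10% | 5.0% | 3 |
| 0.75 | 0.13% | 10.5% | 2.25 |
| 0.5 | 0.20% | 22% | 1.5 |
| 0.25 | 0.40% | 47% | 0.75 |
| 0.1 | 1.0% | 74% | 0.3 |
| 0 | none | 100% | 0 |

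The table shows how the bound depends on capture. It does not estimate the bias in this study.

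**The case against.** The strongest reply is that definitions are not final. Section 9.3.3 leaves per-database definitions to the SAP, section 9.4.1 ties finalisation to the fields obtained through licensing, and the ENCePP checklist marks outcome information as still to come in the SAP. This carries limited weight. The section 9.3.3 sentence concerns covariates and refers to Appendix 3, whereas section 9.3.2 calls the Appendix 2 list pre-specified for the outcomes. The SAP may correct it, but the rule the protocol states is the wrong one.

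The mitigations are real but partial. Appendix 3 rates suicidality as Limited in every source, so some under-reporting is disclosed. New starts of anti-epileptic, mania and depression medicines are tabulated, but outside the AESI definition. Section 9.7.3.1 plans sensitivity analyses of the definitions only where data and predictors allow. Hospital-record review needs separate permission. Nordic deaths are reported, which does not identify suicide. Checklist item 10.6 marks control of outcome misclassification as not applicable.

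Four stronger readings are tempting, and the documents do not support them:

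- **Routine visits for known epilepsy will be counted as seizure AESIs.** The new-onset rule, the at-risk denominator in section 9.7.3 and the 365-day baseline limit this.
- **The protocol defines the depression AESI as F33.** The row is labelled major depressive disorder and sits among conditions that are also baseline comorbidities. That it serves the AESI is an inference from the absence of any other row.
- **The plan applies the 3-in-3,000 bound to suicidality or serotonin syndrome.** The section 9.5 statement is generic.
- **The list should pick out the drug-caused event.** Section 9.7.4 says, of events before discontinuation, that attribution to the product is not possible, and section 8 asks only for new onset.

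It is also fair to say that the code meanings come from the classification and not from the protocol text. The single seizure row against two variables and the single diagnosis list for US and Nordic data can be seen without them.

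**Conclusion.** The concern holds as a mismatch between the stated outcome definitions and the stated codes. Followed as written, Appendix 2 misses isolated seizures, misses first depressive episodes if the F33 row is the one used, leaves completed suicide without a code in any source, and gives near-zero Nordic counts of suicidality and serotonin syndrome for coding reasons. The size cannot be computed from the documents; the capture fractions above are assumptions. The conclusion rests on the ICD meanings of the codes and on Appendix 2 being applied as section 9.3.2 says. The objective is secondary and the study descriptive, but these rows define its safety outcomes, so they should be corrected before final extraction.

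**What to change.** Amend Appendix 2 so that the AESIs have separate columns for Nordic data (WHO ICD-10) and US data (ICD-10-CM):

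- **Seizure AESI:** first post-index R56.8 (Nordic) or its US equivalents, G41, or G40, in patients with none of these codes at baseline. Keep baseline G40 as the seizure-disorder covariate.
- **Depression AESI:** first F32 or F33 with neither at baseline.
- **Suicidality:** intentional self-harm codes, plus cause of death where a linked death register is available, in addition to the present US codes.
- **Serotonin syndrome:** a syndrome-specific definition where one exists; otherwise report the AESI as not ascertainable in that source.

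Add to section 9.5 that the 3-in-3,000 bound refers to coded events and is not to be used for an AESI that a source cannot code.

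Cost: a code-list amendment and a re-run of the extraction code. Cause of death may need an additional linkage: section 9.4.1 describes death registries as linkable and the Danish section mentions one, but the Finnish, Norwegian and Swedish sections name none. R56 and F32 will admit some non-specific events.
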